### **10.3 Benefits**

There is no promise of benefit to subjects in this study. Depressed subjects may benefit from treatment with escitalopram and may derive additional anti-depressant benefit from the combination of escitalopram and celecoxib. There is no benefit to receiving the MRI scans or to the clinical assessments. The scans and the clinical assessments are performed only for research, and the results are not routinely shared with participants. However, in the event that clinically significant MRI or EKG abnormalities are discovered, subjects will be informed of the finding and referred to their physician. An indirect benefit is contributing to scientific knowledge. This study has the potential to greatly increase our knowledge of inflammation in people with depression and may lead to new treatments.

### **10.4 Risk Benefit Assessment**

There are risks associated with participation in this study, but they are minimal and even rare and it is believed that the benefits of conducting the study outweigh the minimal risk.

Celecoxib has been associated with an increased risk of cardiovascular events in people with cardiovascular disease. To mitigate this risk we will enforce our stringent exclusion criteria for people with cardiac risk factors, monitor blood pressure, assess gastrointestinal safety, appoint an independent data safety monitoring board (DSMB) and conduct this study under an FDA-IND for the use of celecoxib. A separate risk/benefit analysis for the use of celecoxib follows below.

CONFIDENTIAL

Because of these precautions, the addition of Celecoxib is not a greater than minimal risk to participants. We will perform the EKG and cardiac risk assessment following the completion of the initial phase of the study before entering into the celecoxib phase in case their cardiac profile has changed. Our exclusion criteria related to cardiac risk include: lifetime history of cardiac surgery or myocardial infarction; unstable angina; acute decompensated congestive heart failure or class IV heart failure; current significant cardiac arrhythmia or conduction disturbance, particularly those resulting in ventricular fibrillation, or causing syncope or near syncope; uncontrolled high blood pressure; QTc greater than 450msec (by history for subjects with cardiac disease); documented prior stroke; Clinically significant abnormalities on EKG.

Additionally, subjects will have blood pressure monitoring at each visit, as it may be a surrogate for celecoxib thrombotic risk. There is also a risk of boredom and/or fatigue from study visits. There is also a rare risk of breach of confidentiality. We have developed procedures for Protection Against or Minimizing Risks for the participant. To reduce risks to participants, only physicians and scientists with extensive training and experience will supervise and perform procedures. Participants will be closely monitored for any side effects from taking escitalopram. There are significant benefits to the research. This study has the potential to greatly increase our knowledge in the treatment and prevention of Depression. No direct benefits are expected to the participant aside from the satisfaction of participating in a study that addresses an important health issue.

### **10.5 Risk / Benefit Assessment for Celecoxib**

Celecoxib is a purposefully designed non-steroidal anti-inflammatory drug, or pdNSAID, which inhibits the enzyme prostaglandin-endoperoxide synthase 2, also known as cyclooxygenase-2, or COX-2. The cardiovascular hazard of NSAIDs is a direct consequence of their intended mechanism of action, inhibition of COX-2 (8, 9). Seven placebo-controlled trials of structurally distinct NSAIDs specific for inhibition of COX-2 have revealed the increase in cardiovascular complications on these drugs (8). Inhibition of the COX enzymes by NSAIDs causes suppression of prostaglandin (PG) production. PGs play important roles in pain, inflammation and pyresis, but also in platelet function, vascular integrity and the regulation of renal blood flow, volume control and vascular tone

This study exposes patients in the age group of 50-80 years diagnosed with depression to 6 weeks of oral celecoxib 200 mg bid. The factors to consider for the risk assessment are i) thrombotic risk, ii) cardiovascular risk profile at baseline, iii) blood pressure response, iv) co-administration of SSRI & COX-2 inhibitor.

#### **10.5.1 Thrombotic risk and cardiovascular risk profile at baseline**

Reports on the cardiovascular safety outcomes are available from the Adenoma Prevention With Celecoxib (APC) clinical trial which used similar dosing, 200 mg celecoxib bid, as in the present protocol as well as double the dose, 400 mg bid (10). The hazard ratio for the pre-specified composite safety end point “cardiovascular death, nonfatal myocardial infarction, nonfatal stroke, or heart failure” was 2.6 (95% confidence interval [CI], 1.1 to 6.1) in patients taking 200

CONFIDENTIAL

mg celecoxib bid, and 3.4 (95% CI, 1.5 to 7.9) for 400 mg celecoxib bid. Though these risk estimates are derived from studies not designed to test for cardiovascular safety but in the case of APC powered to test the efficacy and safety of celecoxib versus placebo in reducing colorectal adenoma recurrence after polypectomy, the data underscores the dose-dependent increase in cardiovascular risk observed for COX-2 selective inhibitors. Hence, **to mitigate the cardiovascular risk for the participants of this protocol, celecoxib will be administered in the lower dose of 200 mg bid.**

The presence of cardiovascular events in the past medical history elevates the hazard ratio to 8.3% in patients exposed to celecoxib compared to 1.9% for the patients on celecoxib without such a history (10). The difference in hazard ratios observed in users and non-users of low-dose aspirin may convey a similar message: patients taking cardioprotective aspirin indicating a past history of CVD show a higher hazard ratio (4.4%) than patients not on aspirin (2.3%) (10). Therefore, **to mitigate the cardiovascular risk for the participants of this protocol, patients with a past history of cardiovascular disease will be excluded.**

A difference in the cardiovascular risk (and upper gastrointestinal complications) at baseline impacts the risk for major vascular (and gastrointestinal) events during treatment with a selective COX-2 inhibitor (11). As these data estimate the per annum risk, we reached out to the senior author, [name] FRCP FFPH, (11) with the question of the adverse event profile in patients during 0-2 months of exposure to celecoxib in patients > 60 years of age. Of note is, that this overview analysis from individual patient data (11) report on the safety of high doses of celecoxib, i.e. 800 mg per day. [name] pointed out the following:

- In this meta-analysis, there were only 5 trials involving a randomized comparison of celecoxib vs placebo in which at least 1 major vascular event occurred and only 2 trials in which at least 1 symptomatic upper GI event occurred (see (11), Webfigures 15 and 20 from the supplementary material that was published alongside the 2013 Lancet paper (11)).
- In the 5 trials in which a major vascular event (MVE) occurred, at least one MVE occurred for 30 out of 1158 patients randomized to celecoxib 800 mg (during a total of 1819 person-years) compared with 8 out of 1079 patients randomized to placebo (during a total of 1750 person-years), yielding an average event rate ratio of 2.96 (99% CI 1.21 to 7.25) ((11), Webfigure 15). Most of the information comes from the APC trial (23 versus 6 MVEs).
- In the 2 trials in which a symptomatic upper GI event, the respective counts were 16 out of 872 randomized to celecoxib 800 mg versus 11 out of 778 randomized to placebo (RR 1.32, 99% CI 0.45 to 3.86) ((11), Webfigure 20). Again, this mostly derived from the APC trial (13 versus 11).
- Given the very small numbers involved, [name] does not advise to try and subdivide these events further by age or duration of follow-up. But, it is worth noting that the effects of any coxib by duration of follow-up/baseline age were also published in the webmaterial ((11), Webfigures 2, 7, 12 and 13).

In conclusion, absolute numbers of patients in which a cardiovascular (or gastrointestinal) event occurred are too small to estimate the risk for the short-term exposure of 8 weeks in this protocol. **The strategy here to mitigate cardiovascular risk is i) to include patients below a**

CONFIDENTIAL

**Framingham 10-year risk score of 13 (15% 10-year risk), taking into consideration that the 10-year cardiovascular risk in our elderly age group (age 60-80) is estimated at 13.5% in the general population and 15% in patients with cerebrovascular risk factors, and ii) to reduce the upper age for inclusion to 80 years of age..** The feasibility of this approach is drawn from our pilot data in a sample (n=217) of late life depression and controls where we determined the Framingham score in both patients with MDD (who had higher vascular risk scores) and age matched controls: Age 60-65 mean score MDD: 9.0 (10-year stroke risk of 8% vs 7% for general population). Age 65-74 mean score: 12.2 (10-year risk of 13.5% vs average risk = 11%); 75-84 mean score: 16.2 (10-year risk of 23% vs average risk of 20%).

**To explore retrospectively how adverse events relate to differences in drug effects, i.e. inhibition of prostaglandin synthesis, urine spot samples will be collected for prostaglandin metabolite analysis at select time points optionally.**

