## **2.8 Key inclusion criteria**

Inclusion Criteria for all Participants:

- 1) Age 18-80, right-handed male or female, any race;
- 2) Absence of clinical dementia
- 3) English speaking
- 4) Blood pressure not exceeding 150/90 mmHg, treated or untreated
- 5) Normal result on liver-function test
- 6) No history of ulcer disease or GI bleeding
- 7) No renal insufficiency
- 8) Weight greater than 110 lbs

Additional Inclusion Criteria for Depressed Participants:

CONFIDENTIAL

- 1) DSM-IV criteria for MDD
- 2) PHQ-8 Score equal to or greater than 10

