#### **10.1.6 Celecoxib**

Celecoxib has been associated with an increased risk of cardiovascular events in people with cardiovascular disease (Celecoxib package insert). Side effects include nausea, diarrhea, gas, cold symptoms, sore throat, lack of energy, loss of appetite, fever, rash, back pain, and flu-like symptoms, among others. Participants would be instructed to contact study members if severe,

CONFIDENTIAL

serious, or persisting side effects occur. There is a rare risk of stroke or heart attack; however these very serious side effects are greatest risk for those with current clinically significant cardiac disease, and we are excluding these people (clinically significant cardiovascular disease usually includes one or more of the following: cardiac surgery or myocardial infarction within the last 4 weeks; unstable angina; acute decompensated congestive heart failure or class IV heart failure; current significant cardiac arrhythmia or conduction disturbance, particularly those resulting in ventricular fibrillation, or causing syncope or near syncope; uncontrolled high blood pressure; QTc greater than 450msec (by history for subjects with cardiac disease); documented prior stroke; clinically significant abnormalities on EKG.) Celecoxib also has increased risk for gastrointestinal bleeding and hepatic impairment. We will exclude those with current ulcer disease or GI bleeding as well as those with liver function impairment (as determined by a liver function test prior to entry into the study). We are excluding clinically significant cardiovascular disease for the past 6 months.

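### The Framingham limit of 13 that Section 10.5.1 sets to contain celecoxib risk is missing from the eligibility lists, the cardiac exclusions in 10.4 and every place where the score is collected

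*Combined protocol and SAP*

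**What the plan says.** Section 10.5.1 concludes that cardiovascular events in the available trials were too few to estimate the risk of short exposure, and then sets out its response. It begins "The strategy here to mitigate cardiovascular risk is i) to include patients below a" and continues with the limit itself, "Framingham 10-year risk score of 13 (15% 10-year risk". The second measure is "ii) to reduce the upper age for inclusion to 80 years of age".

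The second measure is in the inclusion list in 2.8: "Age 18-80, right-handed male or female, any race". The first is in neither 2.8 nor 2.9. The nearest entry in 2.9 is exclusion 12, which concerns existing cardiovascular disease judged case by case. Exclusions 11 and 24 give the investigator general discretion.

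Section 10.4 promises "To mitigate this risk we will enforce our stringent exclusion criteria for people with cardiac risk factors" and then lists them: "Our exclusion criteria related to cardiac risk include: lifetime history of cardiac surgery or myocardial infarction", followed by other existing cardiac conditions, uncontrolled blood pressure, QTc, prior stroke and EKG findings. No risk score is listed.

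The score is collected in three places, none of which attaches a threshold or an action:
- 5.2 includes Framingham questions at the screening visit.
- 5.3 describes a vascular risk factor (VRF) total score for each subject.
- The flow-chart in 12.1 schedules it at the in-person screen and at week 6.

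**The concern.** The two measures are presented as a pair, and only one became an eligibility criterion. Staff who work from 2.8 and 2.9, or from the cardiac list in 10.4, would find nothing to stop a depressed patient with a score of 13 or more from being enrolled and randomised to celecoxib. Section 10.5.1 says that such a patient is not to be included.

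The limit carries weight in the safety argument. The same section cites a hazard ratio of 2.6 (95% CI 1.1 to 6.1) for a composite cardiovascular endpoint at this trial's dose of 200 mg twice daily. It cannot quantify the risk of short exposure, so it relies on limits such as this one, together with dose, age, history exclusions, blood pressure checks and the DSMB. Among these, the score limit is the one numeric rule on predicted risk in a patient who has had no event. Celecoxib goes to at most 50 of the 100 depressed patients at randomisation (1.1), and later to placebo non-remitters who enter the open-label phase (2.2).

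**Working it through.** **Comparing the texts.**

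| Place | Upper age 80 | Framingham below 13 |
|---|---|---|
| 10.5.1, mitigation strategy | stated | stated |
| 2.8, inclusion | stated (18-80) | absent |
| 2.9, exclusion | not needed | absent |
| 10.4, cardiac exclusions | not a cardiac item | absent |
| 5.2, screening visit | not applicable | score taken, no limit |
| 5.3, description of the score | not applicable | no limit |
| 12.1, flow-chart | not applicable | screen and week 6, no limit |

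Section 10.1.6 also lists cardiac exclusions without a score ("We are excluding clinically significant cardiovascular disease for the past 6 months"). It deals with clinically significant disease, where a predicted-risk score would not be expected, so I give its silence little weight.

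**Is the limit coherent as written?** The plan equates a score of 13 with a 15% 10-year risk. Two pilot pairs in 10.5.1 bracket 13: score 12.2 with 13.5%, and score 16.2 with 23%.
- Linear: 13.5 + (13 - 12.2)/(16.2 - 12.2) × (23 - 13.5) = 13.5 + 0.2 × 9.5 = 15.4%.
- Log-linear: 13.5 × (23/13.5)^0.2 = 15.0%.

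Both agree with the stated 15%, so the limit and the pilot scores are on one scale.

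**Would it bind?** Pilot mean minus the limit:
- Ages 60-65: 9.0 - 13 = -4.0.
- Ages 65-74: 12.2 - 13 = -0.8.
- Ages 75-84: 16.2 - 13 = +3.2, from "75-84 mean score: 16.2 (10-year risk of 23% vs average risk of 20". On the risk scale this is 23% - 15% = 8 percentage points.

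The top band runs past the age limit. Interpolating between the band midpoints 69.5 and 79.5 to age 77.5 (the middle of 75-80) gives 12.2 + (8/10) × 4.0 = 15.4. This is still 2.4 above the limit, but it is only a straight line through two means.

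**Why no patient count follows.** Section 10.5.1 gives no SD, no age mix for this trial and no scores below age 60. As an illustration only, assume normal scores, so that the share at or above 13 is 1 - Φ((13 - mean)/SD). With an assumed SD from 3 to 6, the shares are 9% to 25% at 60-65, 40% to 45% at 65-74, and 86% down to 70% at 75-84. These describe a pilot sample of late-life depression and controls (n=217). Only the 60-65 mean is labelled as MDD, and the documents do not say whether this trial's exclusions had been applied to that sample.

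**The case against.** The strongest reply is that the limit is already in the protocol and that this is a matter of placement. It is in bold in 10.5.1 and worded as an inclusion rule. Section 10.4 says that a separate celecoxib analysis follows, and that analysis is 10.5. The lists in 2.8 and 2.9 are headed as key criteria. Other binding rules also sit outside them: the MMSE minimum of 26 in 5.3, the control HAMD maximum of 7 in 5.2 and the claustrophobia exclusion in 10.2.

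This part stands: absence from the lists does not make the rule inoperative. A reader might infer that patients at or above 13 will be given celecoxib, but nothing in the documents shows how staff decide eligibility, and exclusions 11, 12 and 24 leave the investigator room to refuse. What the reply does not answer is the contrast within the protocol. The MMSE and HAMD limits are stated where the test is described or given, and the Framingham limit is not. Section 10.4 sets out cardiac exclusions specifically and still omits it.

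The second reply is that the sentence may be a remnant. Section 10.5 speaks of ages 50-80, 10.5.1 of ages 60-80 and 8 weeks of exposure, and 10.5.2 of a Phase 2. Section 10.5.2 also says that the inclusion and exclusion criteria had proved too demanding. That is a live reading. However, the amendment described there makes only 24-hour ambulatory monitoring optional and does not withdraw the limit. If the limit has been dropped, 10.5.1 still relies on it, so the text needs correcting on either reading.

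A reader might also infer that 10.5.1 requires the limit to be met again before open-label celecoxib. It does not: the rule concerns inclusion. Section 10.4 asks for a repeat EKG and cardiac risk assessment at that point, with no score attached.

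**Conclusion.** The point holds as an inconsistency over a safety threshold. A depressed patient scoring 13 or more can satisfy 2.8, 2.9 and the list in 10.4 while failing 10.5.1. That rests on the text alone and is firm. It has no bearing on type I error, power or sample-size calculations.

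The practical size is not known. The pilot means suggest that the limit would matter mainly from the late sixties upward, provided that the pilot sample resembles the patients screened here. The documents support neither a count of affected patients nor a claim that the limit would be disregarded, and whether it is still in force is for the sponsor to say. It should be corrected because it concerns who may receive celecoxib and the correction is cheap.

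**What to change.** If the limit is still intended, add a criterion of Framingham VRF score below 13 at screening to the depressed-participant criteria in 2.8 or 2.9, and add the same item to the cardiac list in 10.4. Naming the VRF score ties the rule to the instrument described in 5.3. If the limit has been withdrawn, delete it from 10.5.1 and revise the risk-benefit statement that relies on it.

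As an optional extension, the same value could be used in the cardiac risk assessment that 10.4 requires before open-label celecoxib, since 12.1 already repeats the score at week 6.

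The cost is a few lines of text and no new assessment. The real downside is recruitment: fewer older depressed patients would qualify, in a study that reports enrolling only 2 patients in 2 years under its initial strategy (10.5.2). Controls receive no drug and need no limit, although 2.5 matches them on vascular risk factors, so their selection would follow that of the depressed group.

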#### **10.5.2 Blood pressure**

The risk of NSAIDs to induce hypertension (12, 13), sodium retention (13) and edema (13) is well recognized (14-17), but it remains unclear why some patients develop such complications and others do not. Factors associated with this risk are age, co-morbidity, preexisting hypertension and elements of drug exposure to selective COX-2 inhibitors. Latter includes dose, attained plasma concentrations, duration of action and dosing and the degree of selectivity for COX-2.

Retrospective analyses of blood pressure responses have been performed in most NSAID trials of large populations and/or those involving extended drug exposure, although these are usually not based on rigorous (or, in some cases, not even pre-specified) blood pressure measurements. In some studies, the incidence of hypertension has been recorded merely as reported adverse events or by retrospectively defined changes from baseline. Based on these assessments, all NSAIDs have increased blood pressure or induced hypertension within diverse study populations, although this appears to relate to COX-2 selectivity (confounded with drug exposure; (9)). Perhaps unsurprisingly, the rates in blood pressure increase were highly variable across studies and conditioned by the specific characteristics of the study population and by recording methods. However, the lack of information from rigorously designed and sufficiently sized trials limit any conclusions about the relative likelihood of hypertension on specific inhibitors or in subpopulations.

Only a small number of clinical trials – some of which were not powered to detect small changes – have assessed prospectively the effects of COX inhibition on blood pressure control. Of note is that young, healthy individuals are unlikely to experience an increase in blood pressure in response to traditional (t)NSAIDs, such as naproxen or ibuprofen or purposefully-designed, selective COX-2 inhibitors, like rofecoxib or celecoxib based on these studies. Older, normotensive subjects and patients with controlled, stable hypertension can be expected to have average increases of 3-5 mmHg in systolic blood pressure (18-22) with an incidence of above average responses (as defined by an increase of 20 mmHg in systolic blood pressure and a systolic blood pressure above 140 mmHg) ranging from 7-17 %. As one would expect,

CONFIDENTIAL

hypertensive responses to COX-2 selective inhibitors were reported to be more likely in patients with elevated blood pressure as a pre-existing condition (23).

A number of retrospective studies, RCTs, and database studies, as recently reviewed (24), suggest that SSRIs including escitalopram have an overall neutral impact on the cardiovascular system including blood pressure. In a randomized clinical trial using fixed-dose escitalopram, 10 mg/d, over a period of 8 months, hypertension was the reason for discontinuation in only n=2 out of n=274 (0.7%) escitalopram-treated patient (25).

Age has an physiological effect on the glomerular filtration rate (GFR), quantified as a decline in GFR by 0.4 ml/min/year (26). COX-2 inhibitors' renal effects are a decline in the GFR (27) and an alteration of the feedback mechanism which controls renin release (28). Thus, the noted increase in aldosterone concentrations after escitalopram administration - 261±36 pmol/liter at baseline, 269±38 pmol/liter at 2 weeks, and 282±40 pmol/liter at 6 weeks (p=0.04) (29), by itself functionally not associated with changes in blood pressure in this study of normotensive males with depression (29) - might sensitize the reno-vascular system for hypertensive responses under conditions of celecoxib co-administration.

Taking the consideration outlined above into account, **our initial strategy to mitigate this risk was to identify the patients responding to celecoxib administration with an above average increase in blood pressure. The paradigm to detect such an above average signal was the use of continuous 24-hour ambulatory blood pressure monitoring (ABPM) before the start of their enrollment to establish a baseline, and under steady state conditions of celecoxib plasma drug concentrations, i.e. one to two weeks after start of the study; ABPM at the end of the study was planned to collect further safety and interventional data. Patients demonstrating an elevation of 10 mmHg in mean daytime and nighttime systolic blood pressure at 1-2 weeks after the start of the study compared to the mean daytime and nighttime systolic blood pressure at baseline and the mean daytime (that is out of bed times) systolic blood pressure is  $\geq 150$  mmHg were instructed to discontinue trial medication and excluded from the study and instructed to see their primary care physician for further evaluation and follow up.**

**However, using this initial strategy we were only able to enroll n=2 patients during the past 2 years, concluding that the in-/exclusion criteria and protocol procedures, in particular the 24-hour ambulatory blood pressure measurements, are too demanding for the patient cohort under study. Patient screening interviews conducted by the clinical study coordinators reflected this notion among the majority of patients potentially eligible for study inclusion.**

[figure not shown]
**Therefore, to increase enrollment, we amend the protocol to make optional the 24-hour ambulatory blood pressure monitoring, thus focusing on the weekly in-office blood pressure measurements as described below to screen primarily for the risk of blood pressure elevation.**

A similar approach to risk detection was taken in the largest prospectively randomized clinical study on NSAIDs (Nissen SE et al. N Engl J Med. 2016 Dec 29;375(26):2519-29.

CONFIDENTIAL

Cardiovascular Safety of Celecoxib, Naproxen, or Ibuprofen for Arthritis. PMID: 27959716) where patients with osteoarthritis or rheumatoid arthritis and with elevated cardiovascular risk or established cardiovascular disease received either a high dose of ibuprofen or naproxen or a low to medium dose of celecoxib. Data on blood pressure suggests that less than 0.1% of patients exposed to NSAIDs experience hypertensive urgencies or emergencies at 45 days into dosing, which is the planned duration of celecoxib exposure for the current study. The incidence of blood pressure related events did not exceed 0.6% after 30 months of NSAID treatment.

Time to first hospitalization for hypertension in PRECISION (Ruschitzka F et al. Differential blood pressure effects of ibuprofen, naproxen, and celecoxib in patients with arthritis: the PRECISION-ABPM (Prospective Randomized Evaluation of Celecoxib Integrated Safety Versus Ibuprofen or Naproxen Ambulatory Blood Pressure Measurement) Trial. Eur Heart J. 2017 Nov 21;38(44):3282-3292. PMID: 29020251)

Regression lines were added manually per visual inspection to extrapolate the NSAID-exposure-related event risk at 45 days of administration.

**In the case that patients opt in for the 24hr APBM, patients' activity patterns during the 24 hour ABPM sessions, in particular in- and out-of-bed times to differentiate the diurnal profile of blood pressure changes during day- and nighttime, will be recorded by two different methods, paper and pencil logs and body actigraphy.**

CONFIDENTIAL

This material is the property of the University of Pennsylvania.

**In-office blood pressure measurements (in triplicates 5 minutes apart after a 5 minute resting period) will continue at weekly intervals throughout the study. In the case that all systolic blood pressures taken on  $\geq 2$  separate office visits are  $\geq 150$  mmHg systolic blood pressure or  $\geq 90$  mmHg diastolic blood pressure, a follow up 24-hour ABPM will be scheduled within one to two weeks. Here, the same criteria for study exclusion, as outlined above, will be applied.**

The reference systolic and diastolic blood pressure of 150/90 mmHg in people aged 60 years and older has recently been recommended in the “JNC8 evidence-based guideline for the management of high blood pressure in adults 2014” (30).

**In the case that patients opt in for the 24hr APBM, the benefit to patients is the extensive phenotyping of their blood pressure response to celecoxib. Patients exhibiting an above average blood pressure response to celecoxib will be advised to be cautionary in particular when taking over-the-counter or prescription NSAIDs for longer periods of time. In addition, the primary care physician will be advised to monitor blood pressure in such patients.**

A challenge will be the high prevalence of hypertension in this age group, estimated at approximately 65% of men and 75% of women by age 70 years (31). Study enrollment can be offered to this patient cohort provided that blood pressure is adequately controlled with life style changes and/or anti-hypertensive pharmacotherapy. This option will also be offered to patients initially excluded from the study or excluded from the study due to elevated blood pressure. Here, the benefit to patients is that their blood pressure is monitored over periods of 24 hours on multiple occasions, a diagnostic tool less common in the primary care setting. This is expected to actively engage patients in the control of their blood pressure, which is beneficial across all ages (32).

High salt diet and dehydration are two conditions known to induce COX-2 expression in renal medullary interstitial cells (33-36), which play an important role in adaptive regulation of arterial pressure. Resultant vasodilator COX-2 products contribute to the regulation of medullary blood flow (MBF), which drives pressure natriuresis and diuresis. In mice, COX-2 inhibition and nonselective COX-inhibition (37), reduces acutely MBF, sodium excretion and urine volume (38). Coincident challenge of the renal autoregulatory mechanisms by vasopressors, excessive salt intake or volume depletion results in a rise in systemic arterial pressure (38, 39). This is consistent with clinical observations in young and healthy populations in which both nonselective COX inhibition and selective COX-2 inhibition have no effects on arterial pressure despite transient changes in GFR and sodium handling on initiation of dosing, while elderly volunteers show a depression of MBF and an increase in blood pressure (40). To mitigate the risk for a diet-drug interaction on blood pressure, patients will be screened for dietary salt intake per 24-hour dietary recall administered by the CTRC bionutrition core. If the daily salt intake exceeds 1.5 g (<http://www.cdc.gov/salt/>), the patient will receive dietary recommendations to follow a sodium-deplete diet for the duration of exposure to the COX-2 inhibitor in Phase 2. Furthermore, patients will be instructed how to prevent dehydration. This will be achieved by having the patients log their intake of fluids (type, volume) which will be reviewed and, where required, adjusted to meet the Institute of

CONFIDENTIAL

**Medicine's recommended 13 cups (3 liters) of total beverages a day for men or 9 cups (2.2 liters) of total beverages a day for women**  
(<http://www.iom.edu/Activities/Nutrition/SummaryDRIs/DRI-Tables.aspx>).

